#### Analysis Sets

In order to assess sensitivity on efficacy analysis an additional analysis population will be defined. Modified Intention-To-Treat population will be defined as: all included patients who received at least one dose of the study medication and performed at least Visit 2 and Visit 3 laboratory assessments under the same LT4 dose with a valid TSH value.

#### Baseline covariates

Since the repeated measures analysis will be performed only on two time points (one baseline and one post baseline), the models will not include the basal value also as additional covariate for the analysis.

## **4.1 SAMPLE SIZE**

A sample size of 48 subjects had 70% power to detect a difference in means of TSH of 0.7, assuming a standard deviation of differences of 1.9, using a paired t-test with a 0.050 two-sided significance level. To account for a drop-out and dose adjustment rate of about 20%, a maximum number of 60 subjects were to be included in the study (Tirosint® treatment phase).

The study was early terminated with 47 patients included in the Tirosint ® treatment phase and 45 patients completed, due to the COVID-19 pandemic outbreak.

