## **4 TRIAL DESIGN**

This will be an open-label, phase IV study.

Enrolment will be stopped as soon as 48 patients are completed or 60 patients are included in the Tirosint treatment phase, whatever comes first.

Adult patients with a history of hypothyroidism due to total thyroidectomy, who are on stable doses of levothyroxine tablets (between 88 and 250 mcg daily) for at least 6 weeks before screening visit and with a history of gastroesophageal reflux disease (GERD) or associated gastrointestinal issues on prescription (Rx) PPIs (i.e. omeprazole  $\geq$  20 mg daily, or esomeprazole  $\geq$  20 mg daily, or lansoprazole  $\geq$  15 mg daily, or dexlansoprazole  $\geq$  30 mg daily, or pantoprazole  $\geq$  40 mg daily, or rabeprazole  $\geq$  20 mg daily) for at least 8 weeks before screening visit will be included in the study.

During the screening visit, subjects (holding their morning dose of LT4) will undergo screening serum measurements for TFTs (TSH, FT4, free T3 [FT3], total T3 [TT3]), along with a physical examination. Subjects complying with inclusion/exclusion criteria will enter a run-in period, in which they will continue taking their levothyroxine and PPI medications as per prescription, at their current dose. Should the patient require LT4 dose adjustment at screening visit, it will be possible to re-screen the patient until TSH normalization under the new dose.

Four to 6 weeks later (from screening or last re-screening), subjects (fasting and holding their morning dose of LT4) will undergo baseline serum measurements of TSH, FT4, FT3, TT3, as well as total T4 (TT4), creatine phosphokinase (CPK), sex hormone binding globulin (SHBG), ferritin, angiotensin converting enzyme (ACE) level, and lipid panel (triglycerides [TG], total cholesterol [TC], high-density lipoproteins [HDL], low-density lipoprotein [LDL], and very-low-density lipoproteins [VLDL]) as baseline thyroid function related serum laboratory assessments. Patients will then be switched to Tirosint® capsules at the same daily dose.

Patients will remain on Tirosint® for 12 weeks (time frame allowed: 11-13 weeks) and will continue their regular intake of Rx PPI, throughout the whole study duration, according to prescription.

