## **5 SELECTION OF POPULATION**

### **5.1 Subjects selection**

A maximum number of 60 adult patients will be enrolled in this study, in order to have at least 48 patients completed.

The Clinical Investigator is to give his/her approval to the participation of each subject in the study on the basis of acceptable medical history and findings in the physical examination and laboratory investigations which comply with the inclusion/exclusion criteria below.

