### *11.3.1 Sample size*

A sample size of 48 subjects will have 70% power to detect a difference in means of TSH of 0.7, assuming a standard deviation of differences of 1.9, using a paired t-test with a 0.050 two-sided significance level.

To account for a drop-out and dose adjustment rate of about 20%, a maximum number of 60 subjects will be included in the study (Tirosint® treatment phase).

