### 4 STUDY DESIGN

This was an open-label, phase IV study.

Enrolment was to be stopped as soon as 48 patients were completed or 60 patients included in the Tirosint treatment phase, whatever came first.

Adult patients with a history of hypothyroidism due to total thyroidectomy, who were on stable doses of levothyroxine tablets (between 88 and 250 mcg daily) for at least 6 weeks before screening visit and with a history of gastroesophageal reflux disease (GERD) or associated gastrointestinal issues on prescription (Rx) PPIs (i.e. omeprazole  $\geq$  20 mg daily, or esomeprazole  $\geq$  20 mg daily, or lansoprazole  $\geq$  15 mg daily, or dexlansoprazole  $\geq$  30 mg daily, or pantoprazole  $\geq$  40 mg daily, or rabeprazole  $\geq$  20 mg daily) for at least 8 weeks before screening visit were included in the study.

During the screening visit, subjects (holding their morning dose of LT4) underwent screening serum measurements for TFTs (TSH, FT4, free T3 [FT3], total T3 [TT3]), along with a physical examination. Subjects complying with inclusion/exclusion criteria entered a run-in period, in which they continued taking their levothyroxine and PPI medications as per prescription, at their current dose. Should the patient require LT4 dose adjustment at screening visit, it was possible to re-screen the patient until TSH normalization under the new dose.

Four to 6 weeks later (from screening or last re-screening), subjects (fasting and holding their morning dose of LT4) underwent baseline serum measurements of TSH, FT4, FT3, TT3, as well as total T4 (TT4), creatine phosphokinase (CPK), sex hormone binding globulin (SHBG), ferritin, angiotensin converting enzyme (ACE) level, and lipid panel (triglycerides [TG], total cholesterol [TC], high-density lipoproteins [HDL], low-density lipoprotein [LDL], and very-low-density lipoproteins [VLDL]) as baseline thyroid function related serum laboratory assessments. Patients were then switched to Tirosint® capsules at the same daily dose.

Patients were to remain on Tirosint® for 12 weeks (time frame allowed: 11-13 weeks) and were to continue their regular intake of Rx PPI, throughout the whole study duration, according to prescription. Halfway through the Tirosint® treatment period (time frame allowed: 5-7 weeks), subjects reported to the clinical center and (holding their morning dose of LT4) underwent intermediate serum measurements of TSH, FT4, FT3, TT3, for safety assessment.

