## 7 VARIABLES OF INTEREST

### 7.1 EFFICACY VARIABLES

#### 7.1.1 Primary efficacy variables

The primary efficacy variable is the serum levels of TSH.

Serum levels of TSH will be measured at screening visit(s), at baseline, halfway through the treatment period and at the final visit.

The serum levels of TSH recorded after changes in LT4 dose will not be considered for the analysis.

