##### 9.4.1 Primary efficacy analysis

The primary efficacy endpoint is the change in serum levels of TSH at the end of the 12-week treatment period with Tirosint® capsules vs baseline.

A mixed model ANCOVA repeated measures model will be used to test differences in means of TSH level at Visit 4 vs baseline visit. As covariates will be considered the following baseline variables: Age, Sex, BMI and the prescribed Tirosint® dosage (dose/Kg). Unstructured covariance structure will be used (If a different type of covariance structure will be used details will be provided).

Normal distribution for the TSH data will be tested with Shapiro Wilks.

If TSH data results not to be distributed as a normal distribution the following methods will be applied:

- Data will be log transformed and analyzed with the ANCOVA repeated measures model described above.

The TSH level at each time point will also be summarized as continuous variable.

The primary efficacy analysis will be performed on data with missing values replaced with LOCF method and on original data (values recorded after changes in LT4 dose will not be considered in either case).

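### Does SAP 4.1 need a new power figure and a count of usable TSH pairs now that only 45 patients completed?

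*SAP*

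**What the plan says.** SAP 4.1 repeats the protocol's calculation: "A sample size of 48 subjects had 70% power to detect a difference in means of TSH of 0.7", with an SD of the differences of 1.9 and a two-sided paired t-test at 0.05. The allowance for losses is in Protocol 11.3.1: "To account for a drop-out and dose adjustment rate of about 20%, a maximum number of 60 subjects will be included". SAP 4.1 then reports that the trial ended early with 47 patients in the treatment phase "and 45 patients completed, due to the COVID-19 pandemic outbreak".

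The recruitment rule counts completers. Protocol section 4 says "Enrolment will be stopped as soon as 48 patients are completed or 60 patients are included in the Tirosint treatment phase", SAP section 4 repeats this in the past tense, and Protocol 5.1 gives the purpose of the cap of 60 as "in order to have at least 48 patients completed".

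Three other provisions decide who has a usable endpoint:

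- Protocol 6.2 keeps a patient in the study when the LT4 dose is adjusted after a control visit.
- SAP 7.1.1 says "The serum levels of TSH recorded after changes in LT4 dose will not be considered for the analysis".
- SAP 9.4.1 says "The primary efficacy analysis will be performed on data with missing values replaced with LOCF method and on original data".

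**The concern.** In the sample-size calculation, 48 is the number left after both drop-out and dose adjustment, so it means 48 patients with a same-dose TSH pair. The recruitment rule and the account of early termination count completers, which is a different quantity. A patient whose dose is changed on the Visit 3 result can attend Visit 4, count among the 45, and have no Visit 4 TSH that may be analysed.

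The SAP version history runs from September to December 2021, and section 4.1 describes the termination in the past tense. Its authors therefore knew that 48 pairs were out of reach when they left 70% as the only power figure. No analysis set supplies the missing count. The per-protocol set requires completion without a same-dose condition, and the modified ITT set requires same-dose values at Visits 2 and 3, not Visit 4. A reader could take 70% as the power of the trial as run and so misjudge a non-significant result.

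**Working it through.** **Inputs (SAP 4.1).** Mean difference 0.7, SD of differences 1.9, two-sided alpha 0.05, 48 patients, about 20% loss, cap of 60. Achieved: 47 included, 45 completed.

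**Step 1: reproduce the plan.** For n pairs the paired t statistic has n − 1 degrees of freedom and noncentrality (0.7/1.9) × √n. Power is the probability that a noncentral t variable falls outside ± t(0.975, n − 1).

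- n = 48: noncentrality 0.3684 × 6.928 = 2.552, critical value 2.012, power 70.5%. The smallest n reaching 70% is 48.
- Inflation: 48/(1 − 0.20) = 60.

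Both planning figures are right.

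**Step 2: the same test at smaller numbers.** The half-width of the 95% interval is t(0.975, n − 1) × 1.9/√n.

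| Pairs | Basis | Power | Difference detectable with 70% power | 95% CI half-width |
|---|---|---|---|---|
| 48 | plan | 70.5% | 0.70 | 0.55 |
| 47 | all included patients have an endpoint | 69.6% | 0.70 | 0.56 |
| 45 | all completers usable | 67.6% | 0.72 | 0.57 |
| 43 | assumes 2 completers lost to dose change | 65.6% | 0.74 | 0.58 |
| 40 | assumes 5 lost | 62.3% | 0.77 | 0.61 |

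On the documented counts the fall is 70.5 − 67.6 = 2.9 points. Each further lost pair costs about 1 point (67.6% at 45, 66.6% at 44). The losses of 2 and 5 are assumptions.

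**Step 3: who is lost, by version of the analysis.**

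- *LOCF data.* A patient adjusted on the Visit 3 result has a Visit 3 TSH on the unchanged dose. Under SAP section 8 that value is carried forward to replace the excluded Visit 4 value, so this patient costs no pair. Only an adjustment before any same-dose TSH on treatment would leave no such value to carry.
- *Original data.* The pair is lost, but the patient is not. SAP section 4 (changes from protocol) and SAP 9.4.1 make baseline one of the two response times in a mixed model, so a patient with only a baseline value stays in the likelihood. As an illustration, take 40 pairs plus 7 baseline-only patients, equal variances and correlation r. The ratio 2(1 − r) / [(1 − r²)/40 + (1 − r)²/47] gives the equivalent number of pairs: 42.2 at r = 0.3, 41.5 at r = 0.5 and 40.9 at r = 0.7. The gain is small, but it shows that the pair count is not the n of the model.
- Forty-five is not a strict ceiling either. Protocol 7.4 asks for a final visit with TSH from patients who drop out.

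**Step 4: what the planned outputs already show.** Protocol 11.3.6 requires the 95% confidence interval for the primary analysis. SAP 9.5.1 adds an interval on the mean change of each laboratory parameter. SAP 9.2 provides dispositions by visit and by analysis population. SAP 9.4.2 gives the number and percentage of patients needing an LT4 dose change.

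**The case for a change.** The strongest case for a change is that the plan never commits to the one count on which its sample size was based. If the planning loss of 20% had applied to the 47 included, 47 × 0.8 = 37.6 pairs would remain, and power at 37 to 38 pairs would be 58.8% to 60.0%. For an uncontrolled trial planned at only 70%, that bears on how a null result is read, and a sentence would cost little. Nor is this the discredited kind of post-hoc power: it uses the planning effect and SD, not the observed ones.

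Part of this stands. Completion does not guarantee a usable Visit 4 TSH, and the same-dose pair count is not a named output. Stating in the report how many Visit 4 values were observed on the unchanged dose, and how many were carried forward, would be good practice.

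The rest is weaker. The 37 to 38 pairs come from applying a planning rate, not from anything observed; the documents show 2 of 47 patients not completing and give no number adjusted. Completion is not left wholly open, because Protocol 7.4 ties it to Visit 4. The added power figures would describe a raw-scale paired t-test, whereas SAP 9.4.1 specifies a covariate-adjusted mixed model, log-transformed if normality fails. One sentence giving the number with an unchanged-dose Visit 4 TSH could not serve both versions of the analysis, because patients added by LOCF have no such value.

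**Conclusion.** No change to the plan. SAP 4.1 contains no wrong figure: 70% belongs to 48 patients, is put in the past tense as a planning value, and stands beside a plain statement of the shortfall. The recruitment rule did not cause that shortfall, since the pandemic ended the trial before either limit was reached.

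What remains is a reporting detail. On the documented counts it amounts to about 3 points of power and 0.02 in interval half-width, assuming the planning difference of 0.7, the SD of 1.9 and a usable pair from all 45 completers. That is no more than the uncertainty in the SD itself: 48 pairs with an SD of 1.97 give 67.4%. A larger fall would need a number of dose-adjusted completers that the documents do not state, and would bear mainly on the original-data analysis. With enrolment closed, no test, estimate or conclusion depends on a restated power. The confidence interval will show the precision achieved, and analysts can give the pair counts in the report without amending the SAP.

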## **4.2 RANDOMISATION**

Not applicable. This is an open label non-randomized study.

## **5 DEFINITIONS AND DATA CONVENTIONS**

### Age

Age will be calculated in decimal form as portion of the date of screening visit minus the date of birth, divided by 365.25 days per year, and then rounded down, that is:

$$\text{Age (years)} = \text{Floor}((\text{date of screening visit} - \text{date of birth}) / 365.25).$$

Body Mass Index (BMI)

BMI will be computed using the following formula:

$$\text{BMI} = \text{Body Weight (kg)} / (\text{Height (m)})^2$$

Daily dosage

Daily dosage (mcg) will be computed for each patient as:

$$\text{Daily Dosage} = \left( \frac{\sum_{i=1}^7 (\text{daily dosage}_i [\text{mcg}])}{7} \right)$$

where “i” is the day of the week.

Daily dosage/Body Weight

Daily dosage/Body Weight (mcg / kg) will be computed for each patient as:

$$\text{Daily Dosage/Body Weight} = \frac{\left( \frac{\sum_{i=1}^7 (\text{daily dosage}_i [\text{mcg}])}{7} \right)}{\text{Weight [kg]}}$$

where “i” is the day of the week.

Prior medications

Medications reported with an end date before the first study treatment administration (end date < date of first study treatment administration). As prior medication will be also indicated all medications reported by patients who didn't took the study treatment.

Concomitant medications

Medications reported as ongoing or with an end date after the first study treatment administration (ongoing or end date ≥ date of first study treatment administration).

Treatment-Emergent Adverse Events (TEAEs)

Adverse events who started after the start of the study treatment, adverse events without start date and with an end date after the start of the study treatment or adverse events without start date reported as ongoing (for patients who take at least one dose of study treatment).

Pre-Treatment Adverse Events (PTAEs)

Adverse events started after the subject's inclusion into the study but before the effective study treatment period (start date < date of first study treatment administration).

Serious Adverse Events (SAEs)

Adverse Event judged as serious.

Drug related Adverse Events

Adverse Events with a relationship to treatment reported as "Certain", "Probable" or "Possible".

Adverse events leading to discontinuation

Adverse Events leading to discontinuation is an AE with action taken equal to "Drug withdrawn".

Adverse events leading to death

Adverse Events leading to death is an AE with outcome equal to "Fatal".

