#### 5.4 Withdrawal of subjects

Participation may be discontinued for any of the following reasons:

---

 Checked by medical history

- voluntary subject withdrawal for any reason;
- at the Investigator's discretion (reason should be specified);
- if an adverse event (including worsening of concomitant illness) develops, which is considered by the Investigator as incompatible with the continuation of the study;
- if the administration of a drug which is not permitted according to the exclusion criteria is necessary (this should be discussed between the Investigator and the Sponsor);
- failure to comply with the requirements of the protocol or significant protocol deviation (e.g. inclusion error, evidence of non-compliance with exclusion/inclusion criteria arisen during the study, subject misses study visits or/and is not compliant with drugs intake, etc.);
- if a pregnancy develops;
- lost to follow-up;
- patient death;
- if LT4 dose adjustment is required upon receipt of baseline (V2) laboratory results and before any control visit (interim or unscheduled) is performed;
- if PPIs dose adjustment outside the allowed range is necessary or if PPIs are discontinued.

Subjects who withdraw or are withdrawn from the study after inclusion in the Tirosint® treatment phase (V2) will not be replaced. Subjects who withdraw or are withdrawn from the study before inclusion in the Tirosint® treatment phase (during the run-in phase) will be considered as screening failures.

See section 7.4 for the assessments to be performed in case of early withdrawal.

[figure not shown]

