***Visit 3 - Day 42±7 (Interim visit)***

Halfway through the treatment period (i.e. 35-49 days after V2), the patients will report to the clinical center in the morning, holding their daily dose of levothyroxine and bringing with them their diary as well as the unused, used and partially used boxes of Tirosint, and the box/bottle of the PPI, and will undergo:

- adverse events (AEs) and concomitant medications;
- blood sampling for thyroid function tests (TSH, FT4, FT3, TT3) for safety check;
- Tirosint® capsules return and count to check compliance;
- diary collection and check to verify compliance with LT4 and PPI;
- Tirosint® dispensing;
- diary dispensing;
- remind the patient how to complete the diary and how to comply with the study requirements (i.e. drugs intake, study restrictions, etc.).

The new onset or the worsening of clinical signs/symptoms of hypothyroidism or hyperthyroidism (e.g. palpitations) reported by the patient, if clinically significant, will have to be recorded as adverse events.

Any changes in the concomitant medications, including the PPI product and/or dose will be recorded in the CRF.

If the subject brings it, the PPI box/bottle will be checked to verify changes from the previous visit.

All the used boxes of Tirosint® will be collected by the Investigator, pills will be counted for check of compliance and drug accountability, and the boxes will be stored by the Investigator or Pharmacist separately from unused supplies. Leftover pills cannot be re-dispensed.

Patients will be dispensed sufficient amount of Tirosint® capsules for treatment up to Visit 4.

The patients will be asked to take their morning LT4 dose only after blood sampling and will continue taking the study medications at the prescribed dose.

The date of Visit 4 will be scheduled and patients will be asked to come to the clinical center for the next visit, fasting and holding their morning dose of LT4, and bringing with them their diary, the box/bottle of the PPI that they are on therapy with and the used, partially used, and unused boxes of Tirosint®.

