### 9.5.2 Adverse Events

Adverse events (AEs) intensity and frequency will be analysed during the pre-treatment phase and in the treatment phase until End of Study Visit.

The following summary tables will be provided:

- Adverse Events by SOC and PT;
- Serious Adverse Events by SOC and PT;

- Drug related Adverse Events by SOC and PT;
- Pre-Treatment Adverse Events by SOC and PT;
- Serious Pre-Treatment Adverse Events by SOC and PT;
- Treatment-Emergent Adverse Events by SOC and PT;
- Serious Treatment-Emergent Adverse Events by SOC and PT;
- Drug related Treatment-Emergent Adverse Events by SOC and PT;

Serious adverse events and fatal adverse events will also be listed.

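### The treatment-emergent AE definition has no worsening clause, so a run-in event that worsens on capsules and stays on one record is left out of the treatment-emergent tables

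*SAP*

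**What the plan says.** SAP section 5 sets the two period classes. An event with a start date is treatment-emergent if it falls under "Adverse events who started after the start of the study treatment". An event with no start date is treatment-emergent if it ended after treatment began, or under the clause "adverse events without start date reported as ongoing (for patients who take at least one dose of study treatment". A pre-treatment event is one that began after "inclusion into the study but before the effective study treatment period (start date < date of first study treatment administration". Neither class mentions an increase in severity or a change to serious.

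SAP section 9.5.2 states: "Adverse events (AEs) intensity and frequency will be analysed during the pre-treatment phase and in the treatment phase until End of Study Visit". The tables it names are all by system organ class and preferred term. They cover all AEs, all SAEs, all drug-related AEs, pre-treatment AEs, serious pre-treatment AEs, TEAEs, serious TEAEs and drug-related TEAEs. Serious and fatal events are also listed. No severity table is named.

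Protocol section 10 starts AE collection at consent. Protocol sections 7.3 and 7.4 require, at Visits 2, 3 and 4, that if clinically significant, "The new onset or the worsening of clinical signs/symptoms of hypothyroidism or hyperthyroidism" be recorded as adverse events. Among the withdrawal reasons in Protocol section 5.4 is "if an adverse event (including worsening of concomitant illness) develops". Inclusion is placed at Visit 2 in the study schedule and in section 5.4: "after inclusion in the Tirosint® treatment phase (V2) will not be replaced".

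**The concern.** The run-in lasts 4 to 6 weeks, and the screening period can reach 4 months with re-screening, so some AEs may well be ongoing when the patient changes from tablets to capsules. The protocol treats deterioration of an existing condition as an adverse event, but the SAP does not carry this into its period definitions. Whether a deterioration on capsules counts as treatment-emergent then depends on how the site recorded it: as a continuation of the old entry, or as a new event with its own onset date.

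This matters because the trial has one arm and each patient's baseline on tablets is the control (Protocol section 4). For safety, the comparison available is before versus after the switch, and the TEAE tables are what a reader will take as the capsule-phase experience. A deterioration missing from them makes the capsule phase look better, never worse.

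**Working it through.** The plan gives no figure on this point, so the check applies the SAP section 5 rules literally to test events. Day 0 is both Visit 2 and the first capsule.

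| Event | TEAE? | Pre-treatment AE? |
|---|---|---|
| A. Starts day -10, worsens day 30, kept on one record | No | Yes by the date condition; no if inclusion means Visit 2 |
| B. Same worsening entered as a new AE with onset day 30 | Yes | No |
| C. Starts on the date of first dose | No (not after) | No (not before) |
| D. No start date, ongoing | Yes | No |
| E. No start date, ends day 20 | Yes | No |

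**Cases A and B** are the same clinical course with different classifications; only the record-keeping differs. Neither document says which recording practice applies. The AE form in Protocol Appendix I has one onset, one seriousness code and one severity code per line, and no rule for a line that worsens. The SAE form asks for severity as maximum intensity beside a single onset date, so a serious event on that form can combine a run-in onset with a peak reached on capsules.

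**Where case A still appears.** It is in the all-AE table; in the all-SAE table and SAE listing if it became serious; and in the all-drug-related table if rated related. It is absent from the TEAE, serious TEAE and drug-related TEAE tables.

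**Which period it is assigned to instead.** The condition "start date < date of first study treatment administration" would make case A pre-treatment. The same definition also requires onset after inclusion. If that means Visit 2, as the protocol uses the word, a run-in event began too early to qualify and has no period at all. The SAP plans pre-treatment tables, so run-in events were probably meant to be in them, but the wording does not secure this.

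**Case C** is a separate gap: comparing dates, an event starting on the day of first dose falls in neither class.

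**Size per patient.** The safety population is all included patients, and SAP section 4.1 gives 47. A patient counts once towards the TEAE rate, so an affected patient changes it only if he or she has no other TEAE:

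- 1 patient: 1/47 = 2.1%
- 2 patients: 2/47 = 4.3%
- 3 patients: 3/47 = 6.4%

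**How many patients.** The documents give no AE rate and no worsening rate. As illustration only, let r be the share with a run-in AE ongoing at Visit 2 and w the share of those whose event worsens on capsules. Both are assumed. The expected number is 47 × r × w, and the chance of at least one is 1 − (1 − r × w)^47.

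- r = 5%, w = 5%: 47 × 0.0025 = 0.1 patients; chance 11%
- r = 10%, w = 10%: 47 × 0.01 = 0.5 patients; chance 38%
- r = 20%, w = 25%: 47 × 0.05 = 2.4 patients; chance 91%
- r = 40%, w = 50%: 47 × 0.20 = 9.4 patients; chance above 99%

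A range from 0.1 to 9.4 patients shows only that the number cannot be settled from the documents.

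**The case against.** The strongest reply is that the plan already covers what matters most. Clinically significant worsening of thyroid signs or symptoms, the events most relevant to a levothyroxine formulation switch, must be recorded as AEs at Visits 2, 3 and 4. If entered with their own onset date, they are TEAEs under the present definition. The withdrawal criteria show that worsening of other illness is also regarded as an adverse event. Only the second page of the AE form is reproduced, and the study CRF and its completion instructions are not in the documents, so site practice cannot be checked. Much of this stands. It confines the gap mainly to non-thyroid events, and to thyroid events recorded without a new onset date. It does not close the gap, because nothing in either document requires a new record or a new onset date.

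Four stronger readings are tempting and are not supported:

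- **That classification rests on start date alone.** Events with no start date are classed by end date or ongoing status, and that rule leans towards counting them as TEAEs.
- **That the event is tabulated as pre-treatment at the severity it reached on capsules.** The pre-treatment label is uncertain because of the inclusion wording. For non-serious AEs nothing says the original severity is overwritten, and no severity table is named. Only the SAE form asks for maximum intensity.
- **That a serious deterioration disappears.** It remains in the all-SAE table and the SAE listing; what goes wrong is its period.
- **That the TEAE rate is understated by 2.1 to 6.4 points.** That range is a ceiling for an assumed 1 to 3 patients, none of whom has another TEAE.

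**Conclusion.** The point holds as a definitional gap of minor weight. For AEs with a known start date, SAP section 5 has no worsening clause, and a run-in event kept on one record that worsens or becomes serious on capsules is left out of all three treatment-emergent tables. This follows from the text alone. It becomes an error in the results only if at least one AE was ongoing at first dose, worsened afterwards, and was not given a new onset date. The direction is certain: the missing clause can only lower capsule-phase counts. The size is not derivable. It is nil if no run-in event worsened, and otherwise at most 2.1 percentage points of the TEAE rate per affected patient. In the serious TEAE table a single event could be the difference between a count of one and none, although the all-SAE table and the listing would still show it.

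**What to change.** In SAP section 5, add to the TEAE definition: *or adverse events that started before the first dose and increased in severity, or became serious, on or after the first dose*. Before the analysis, review every AE ongoing at first dose against the AE and SAE forms and source notes to identify these events, and state in the SAP how worsening is represented in the data.

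In the same edit, define pre-treatment AEs as starting from consent rather than from inclusion, so that run-in events have a class, and assign events starting on the day of first dose to one class.

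The cost is a few lines of SAP text and a review limited to AEs ongoing at first dose. The downside is a data query wherever the record holds no date of worsening or no run-in severity. Where one record holds only one severity, the run-in severity may not be recoverable; the event can then be counted as treatment-emergent with its run-in severity reported as unknown.
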